3.4. Multiplicity Adjustment

The overall statistical level is α =0.10 (2-sided). Because 2 dose regimens of HZN-825 will be compared to placebo, a hierarchical testing procedure will be used for multiple comparisons. Therefore, α =0.10 (2-sided) will be used in the analysis. The hierarchical testing procedure will be used for the primary and key secondary endpoint. For the primary endpoint, the BID dose will be tested versus placebo first; if significant, the QD dose will then be tested. If 1 or 2 dose regimens of the primary endpoint are not rejected after completing testing, no further testing will occur. If both HZN-825 doses are statistically significantly better than placebo for primary efficacy endpoint, the testing procedure will continue for the key secondary endpoint and will be similar to that performed for the primary endpoint.

Although p-values will be provided for the other secondary and exploratory endpoints, they will not be used for inferential purposes.

Version 2.0

3.5. Missing Data

In general, missing data will not be imputed unless methods for handling missing data are specified. Exceptions are presented in this document.

The handling of missing or incomplete dates for last dosing date of study drug and AE onset is described in the TLF shells document. Refer to Section 6 for details on how to handle missing data for efficacy analyses.

3.6. Definition of Baseline

Unless otherwise specified, the baseline value (Baseline) is defined as the last non-missing observation prior to the first dose of study drug. The two types of Baseline for the OLE Phase are defined in section 1.1.2. In cases where baseline measurements are taken on the same day as study drug and no times are reported, it will be assumed that these measurements are taken prior to study drug being administered. In cases where multiple measurements are taken on the same day as study drug without time reported, the average of these measurements will be taken as Baseline. Missing baseline evaluations will not be imputed and will be considered missing.

3.7. Study Day

Core Phase

The day of the first dose of study drug administration will be considered as study Day 1. Study day will be calculated as:

For postdose study days: assessment date – first dosing date +1

For days prior to the first dose: assessment date – first dosing date

OLE Phase

The day of the first dose of study drug administration in the OLE Phase will be considered as OLE Day 1. OLE Phase study day will be calculated as:

OLE study day: assessment date – OLE first dosing date +1

3.8. Analysis Windows

For endpoints that present visit-based data, the variables will be summarized based on the scheduled visits with derived analysis visit windows. No visit windows will be derived for the screening period and for PK data. For the visits on and after the 1st dose date, the actual visit date will be mapped to the derived analysis visit windows based on the study day (see Section 3.7).

Visit windows have been constructed so that every observation (unscheduled visits included) collected can be allocated to a specific visit. The actual assessment day will be mapped to the windows defined for each scheduled study visit with following rules:

Version 2.0

- If more than 1 assessment falls within a visit window, the closest non-missing valid assessment to the target day will be used in the analysis.
- If 2 non-missing assessment actual dates are equidistant from the target day, the later visit will be used in the analysis.
- For retest values of laboratory and spirometry data, the retest value (the last valid observation assessed on the same visit day or corresponding to the same visit) will be chosen.

The Analysis Visit Window for the primary endpoint FVC % predicted is shown in Table 1. The details for the other analysis visit window rules will be included in the TLF shells document.

Version 2.0

Table 1. Analysis Visit Windows for Primary Endpoint

Scheduled Visit	Target Day of the Visit	Analysis Visit Window	
Core Phase Analysis			
Baseline	Day 1	Day 1/before 1st dose of HZN-825 or Placebo in the Core Phase	
Week 4	Day 29	Day 2 to 71	
Week 16	Day 113	Day 72 to 155	
Week 28	Day 197	Day 156 to 239	
Week 40	Day 281	Day 240 to 323	
Week 52	Day 365	Day ≥ 324 to Core Phase end date	
OLE Baseline Analysis			
OLE Baseline	Week 52 Visit Date	OLE Day 1/Before OLE 1st dose	
Week 68	OLE Day 113	OLE Day 2 to 155	
Week 80	OLE Day 197	OLE Day 156 to 239	
Week 92	OLE Day 281	OLE Day 240 to 323	
Week 104	OLE Day 365	OLE Day ≥ 324	
HZN-825 Baseline Analysi	S		
HZN-825 Baseline	Day 1	Day 1/Before 1st dose of HZN-825 or Placebo in the Core Phase	
Week 4	Day 29	Day 2 to 71	
Week 16	Day 113	Day 72 to 155	
Week 28	Day 197	Day 156 to 239	
Week 40	Day 281	Day 240 to 323	
Week 52	Day 365	Day 324 to 421	
Week 68	Day 477	Day 422 to 519	
Week 80	Day 561	Day 520 to 603	
Week 92	Day 645	Day 604 to 687	
Week 104	Day 729	Day ≥ 688	

Data from all assessments (scheduled and unscheduled), including multiple assessments, will be included in listings.

The analysis visit windows will also be derived similar to the primary endpoint for other variables, such as laboratory values, vital signs, ECGs, and physical exam findings as needed.

Version 2.0

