# 9.4.6.1.2 Drug-induced Liver Injury

Elevated hepatic transaminases have been evaluated to be an important identified risk with fipaxalparant (HZN-825). The events are mostly non-serious and transient. Refer to Section 9.3.3.1 for criteria regarding trial drug discontinuation due to drug-induced liver injury.

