7.2.3. Shifts Relative to the Baseline Value

For hematology, chemistry, lipids and coagulation, results will be categorized as low, normal, or high based on their normal ranges. If toxicity grading is applicable to the laboratory result, toxicity grades will also be evaluated and assigned to the result. If available, shift tables using categories of toxicity grade comparing laboratory test results from Baseline to each visit will be presented with percentages based on subjects with a non-missing value at baseline and post-baseline visit. For toxicity grading where the grade can be assigned based on a low value and a high value, then both will be presented separately in the table summary.

If toxicity grade is not available, then categories of low, normal, and high will be used for the analogous presentation.

For urinalysis tests, results will be classified as normal or abnormal. Results out of range will be identified as such on subject listings. Shift tables for urinalysis results using categories of normal and abnormal, comparing laboratory test results from Baseline to each visit will be

Version 2.0

presented with percentages based on subjects with a non-missing value at Baseline and post-baseline visit.

Shift plots may be produced for selected laboratory values.

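### Laboratory shift tables run only from Baseline to each visit, so a transient non-liver abnormality can be missing from every by-arm laboratory table

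*SAP*

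**What the plan says.** SAP 3.8 sets the selection rules for by-visit summaries: "For endpoints that present visit-based data, the variables will be summarized based on the scheduled visits with derived analysis visit windows". Unscheduled results are drawn in as well: "Visit windows have been constructed so that every observation (unscheduled visits included) collected can be allocated to a specific visit". Laboratory data are included: "The analysis visit windows will also be derived similar to the primary endpoint for other variables, such as laboratory values".

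Two rules then choose one result per window.

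- The general rule: "If more than 1 assessment falls within a visit window, the closest non-missing valid assessment to the target day will be used in the analysis". A tie goes to the later assessment.
- The retest rule, which begins "For retest values of laboratory and spirometry data, the retest value (the last valid observation assessed on the same visit day" and goes on to include a retest tied to the same visit. That retest is the value chosen. The rule does not ask whether the first result was valid.

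SAP 3.8 does not rank these two rules. For windows other than that of FVC % predicted it adds: "The details for the other analysis visit window rules will be included in the TLF shells document".

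SAP 7.2.3 then states that "shift tables using categories of toxicity grade comparing laboratory test results from Baseline to each visit will be presented". It uses low, normal and high where no toxicity grade exists, and normal or abnormal for urinalysis, always by visit. The numeric summaries in SAP 7.2.1 are also by visit. Protocol 9.6.2.4 plans Extension Phase shift tables by visit too.

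SAP 7.2.2 is the exception. It counts each subject once by the most severe post-baseline value, for AST, ALT, total bilirubin, alkaline phosphatase and GGT.

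**The concern.** A laboratory test is usually repeated because the first result was abnormal. If the repeat stands for the visit, the replacement tends to run towards normal, through regression to the mean or through real recovery. By-visit shift tables built on the selected values then show the subject as normal at that visit.

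Outside the five liver tests, no planned table looks across all post-baseline results for the worst one. This applies to creatinine, creatine kinase, electrolytes, blood counts, lipids, coagulation and urinalysis. Protocol 9.6.1.6 and SAP section 7 plan no inferential tests for safety, so the descriptive tables are what a reader uses to compare arms. An abnormality that came and went between selected values would not be counted by arm in any laboratory table.

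**Working it through.** The plan gives no figure on this point to reproduce. The check applies the SAP 3.8 rules to a worked case and then asks which planned table could recover a dropped value.

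**Inputs.** The target day for Week 16 is Day 113 (SAP Table 1). The first result is Grade 3 and the repeat is Grade 0. Assumption: both fall in the same laboratory window, because laboratory windows are left to the TLF shells, which are not among the documents. First-result days tried: 106, 110, 113, 116 and 120. Gaps to the repeat: 0, 3, 5, 7 and 14 days. That makes 5 × 5 = 25 combinations.

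**Reading A: the repeat is recorded as belonging to the same visit.** The retest rule applies, and Grade 0 is kept in all 25 combinations.

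**Reading B: the retest rule covers same-day repeats only, and an off-day repeat is treated as unscheduled.** In the 5 same-day combinations Grade 0 is kept. In the other 20, the result with the smaller |day − 113| is kept. Examples:

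| First result (Grade 3) | Repeat (Grade 0) | Distances from Day 113 | Kept |
|---|---|---|---|
| Day 113 | Day 116 | 0 and 3 | Grade 3 |
| Day 110 | Day 117 | 3 and 4 | Grade 3 |
| Day 106 | Day 113 | 7 and 0 | Grade 0 |
| Day 106 | Day 120 | 7 and 7, later used | Grade 0 |

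Over the 20 off-day combinations, Grade 3 is kept in 14 and Grade 0 in 6. These counts describe the grid of days chosen and are not probabilities.

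**The reverse case.** The scheduled result on Day 113 is normal, and an unscheduled result on Day 120 is Grade 3 and not labelled a retest. The distances are 0 and 7, so the normal value is kept and the Grade 3 is not tabulated. The nearest-to-target rule alone can therefore drop an abnormality.

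**Which output would still show the dropped value?**

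| Output | Basis | Shows a dropped non-liver value by arm? |
|---|---|---|
| SAP 7.2.1 numeric summaries | by visit | No |
| SAP 7.2.3 shift tables, including urinalysis | Baseline to each visit | No |
| Protocol 9.6.2.4 shift tables (Extension Phase) | each Baseline to each visit | No |
| SAP 7.2.2 liver tables | most severe post-baseline value | Not applicable: five liver tests only |
| Listings (SAP 3.8, 7.2) | all results, abnormal ones flagged | Present by subject, no incidence by arm |

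**Scale.** With 45 subjects per arm (SAP 1.3), and assuming all 45 are in the denominator, one subject missing from an incidence count is 1/45 = 2.2 percentage points, and two are 2/45 = 4.4. This gives the unit of loss. The number of subjects affected is not known.

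**The case against.** The strongest reply is that the gap lies in one table format and that other outputs keep the values. Every result is listed and flagged. A laboratory finding can be an adverse event (Protocol 9.5.5.1.1.1), and SAP 7.1.5.1 tabulates adverse events by maximum severity and at Grade 3 or higher. This stands in part: nothing is lost from the database. But a listing gives no incidence by arm, and the adverse event tables depend on the investigator recording the result as an event.

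A second reply is that the TLF shells may settle the order of the rules. They may. That would not supply a worst-value table, which is a matter for SAP 7.2.3.

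Four stronger readings are tempting, and the documents do not support them.

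- A reader might infer that every abnormality that settles on repeat disappears from the shift tables. The retest rule covers same-visit retests only. For an off-day repeat, the nearest-to-target rule can keep the abnormal value, as the worked case shows.
- A reader might infer that the drug's identified laboratory risk is hidden, because Protocol 9.4.6.1.2 says of raised transaminases that "The events are mostly non-serious and transient". SAP 7.2.2 already counts those tests by worst value.
- A reader might take the close observation in Protocol 9.3.3.1.1 (tests 2 or 3 times weekly) as a measure of how many results compete for one window. That schedule is for liver enzymes and bilirubin, so it does not size the non-liver gap.
- A reader might infer that one arm is understated more than another. The documents give no non-liver retest rate, by arm or overall. They also do not state why laboratory retests are done, so the direction of the loss rests on usual practice.

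**Conclusion.** The point holds as a gap in the safety tabulations. If SAP 3.8 and 7.2.3 are followed as written, a transient abnormality in non-liver chemistry, hematology, lipids, coagulation or urinalysis can be absent from every by-arm laboratory table. A same-visit retest replaces the first value outright. For an off-day repeat the result depends on the days and on a precedence that SAP 3.8 does not state.

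The size of the loss, and any imbalance between arms, cannot be computed from the documents. The primary and secondary efficacy analyses are not in question.

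The conclusion assumes that SAP 7.2.2 draws on all results, since the selection rules in SAP 3.8 are addressed to by-visit summaries. It also assumes that the TLF shells add no worst-value table of their own. The plan already uses the suitable method elsewhere: the worst value for liver tests, and maximum severity for adverse events. Extending it to the remaining laboratory tests would make the plan consistent.

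**What to change.** Keep the by-visit tables as planned. Add to SAP 7.2.3 shift tables from Baseline to the worst post-baseline grade, or category where no grade exists, with low and high shown separately. Use all valid scheduled, unscheduled and retest results, by arm and phase. For urinalysis, the worst category is abnormal at any post-baseline assessment.

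In SAP 3.8, add one sentence stating whether the retest rule or the nearest-to-target rule takes precedence when a repeat falls on a different day from the visit. Whether the by-visit tables show the scheduled value or the retest is then a matter of convention, because the worst-value tables retain the abnormal result either way.

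The cost is one sentence in SAP 3.8, a short addition to SAP 7.2.3 and one more set of tables. No new data are needed.

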At the interim analysis, the IDMC will provide recommendation to select Horizon personnel not involved in the oversight of the trial to facilitate trial continuation and dose selection for future trials. To support decisions on future dose selection and future trial design, a Horizon unblinded team may be established and receive unblinded data and perform ad hoc analyses, as needed. All unblinded data and analysis results made available to the Horizon unblinded team will be archived to allow for any potential post hoc assessments of bias. For additional details, please refer to the IDMC charter and Blinding Maintenance Plan for this trial.

An overview of the Core Phase trial design is presented in Figure 1.

Version 2.0

Figure 1. Schematic of Trial Design – Core Phase

BID=twice daily; QD=once daily

- 1. Subjects will be randomized in a 1:1:1 ratio to receive HZN-825 300 mg QD, HZN-825 300 mg BID or placebo.
- 2. If a subject prematurely discontinues trial drug, he/she will be asked to remain in the trial, participating in the scheduled trial visits through Week 52. If a subject prematurely discontinues trial drug and does not wish to continue in the trial, he/she will be asked to return for a clinic visit and undergo the Week 52 assessments. Subjects not entering the 52-week Extension Phase will return to the clinic 4 weeks after the last dose of trial drug for a Safety Follow-up Visit.
- 3. Visit windows are ±3 days for Week 4, ±7 days for Week 10 to Week 52, inclusive, and ±14 days for the Safety Follow-up Visit.
- 4. Visits at Weeks 2 and 6 are remote (telephone) visits with a ± 3 -day window.
- 5. Subjects who complete the Double-blind Treatment Period (Week 52) may be eligible to enter a 52-week Extension Phase of the trial.

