1.2.3. Design of the Extension Phase of the Trial

[figure not shown]
The Extension Phase of the trial is an optional, open-label, repeat-dose, multicenter extension of the Core Phase. Subjects who complete the Double-blind Treatment Period (Week 52) in the Core Phase of the trial may be eligible to enter this 52-week Extension Phase. Subjects entering the Extension Phase will complete the Week 52 Visit, which will be considered Day 1 of the Extension Phase and will receive their first dose of open-label HZN-825 in the Extension Phase at the clinic and return to the clinic for trial visits at Weeks 56, 62 and 68, then every 12 weeks through Week 104. The Week 52 Visit activities will serve as Baseline for the Extension Phase. Subjects will return to the clinic for a Safety Follow-up Visit 4 weeks after the last dose of HZN-825.

If a subject prematurely discontinues HZN-825, he/she will be asked to remain in the trial, participating in the scheduled trial visits through Week 104. If a subject prematurely discontinues HZN-825 and does not wish to continue in the trial, he/she will be asked to return for a clinic visit and undergo the Week 104 assessments.

An overview of the Core Phase trial design is presented in Figure 2.

Version 2.0

Figure 2. Schematic of Trial Design – Extension Phase

BID=twice daily

- 1. The HZN-825 dose may be modified based on the results of the Core Phase.
- 2. If a subject prematurely discontinues open-label HZN-825, he/she will be asked to remain in the trial, participating in the scheduled trial visits through Week 104. If a subject prematurely discontinues open-label HZN-825 and does not wish to continue in the trial, he/she will be asked to return for a clinic visit and undergo the Week 104 assessments.
- 3. Visit windows are ±5 days for Week 56, ±7 days for Week 62 to Week 104, inclusive, and ±14 days for the Safety Follow-up Visit.
- 4. Visits at Weeks 74, 86 and 98 are remote (telephone) visits with a \pm 7-day window.

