3.9. Reporting Period

The reporting periods for each phase are defined below. For subjects that entered OLE Phase, both OLE Phase and combined study period will be used in reporting.

Core Phase

Treatment period: time from first dose of study drug intake to 28 days after last dose of study drug intake in the Core Phase.

Study period: time from first dose of study drug intake to the end of Core Phase.

For subjects who entered and took any study drug in OLE Phase, the day of their first dose intake in the OLE Phase marks the end of their Core Phase treatment and study period.

OLE Phase

Treatment period: time from first study drug intake in the OLE Phase to 28 days after last dose of study drug intake in the OLE Phase.

Study period: time from first dose of study drug intake in the OLE Phase to the end of OLE Phase.

Combined Study Period

Treatment period: time from first dose of study drug intake (either HZN-825 or placebo) in the Core Phase to 28 days after the last dose in the OLE Phase.

Study period: time from first dose of study drug intake (either HZN-825 or placebo) in the Core Phase to the end of OLE Phase.

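### SAP Table 1 assigns an FVC taken on OLE Day 2 to 57 to Week 68 in one Extension analysis and to Week 52 in the other

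*SAP*

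**What the plan says.** SAP section 3.8, Table 1, has three blocks of FVC windows.

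- **Core Phase:** Week 52 (target Day 365) is "Day ≥ 324 to Core Phase end date". For subjects who enter the extension, section 3.9 says "the day of their first dose intake in the OLE Phase marks the end of their Core Phase treatment and study period".
- **OLE Baseline:** Week 68 (target OLE Day 113) is "OLE Day 2 to 155". Section 3.7 defines "OLE study day: assessment date – OLE first dosing date +1".
- **HZN-825 Baseline:** Week 52 covers study Days 324 to 421 and Week 68 (target Day 477) covers Days 422 to 519. There is no stop at the first open-label dose.

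Subjects entering the extension "complete the Week 52 Visit, which will be considered Day 1 of the Extension Phase" (section 1.2.3). The Core design figure in section 1.2.2 gives the visit tolerance as plus or minus "7 days for Week 10 to Week 52, inclusive". When a window holds several values, "the closest non-missing valid assessment to the target day will be used in the analysis". For ties: "If 2 non-missing assessment actual dates are equidistant from the target day, the later visit will be used in the analysis". Section 3.8 also says that the windows place every observation, unscheduled ones included, at some visit.

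The extension schedule (SAP section 12.2) plans no FVC between the Week 52 visit and Week 68. A subject who stops open-label drug and leaves is asked to come in for the Week 104 assessments, which include spirometry.

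**The concern.** The two Extension analyses use the same FVC measurements, but their windows disagree about values from the first eight weeks of open-label treatment. One block calls such a value a Week 68 result, so a measurement made days after OLE Baseline can be reported as a 16-week change. The other block calls it a Week 52 candidate although it follows open-label dosing. For a subject who had placebo in the Core Phase, that could put an on-drug value at the visit that represents the end of placebo.

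The Core block avoids the second problem by stopping at the Core Phase end date, and the HZN-825-Baseline block does not repeat that stop. One subject could then have different Week 52 values in two tables of the same report.

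**Working it through.** **1. Reproduce the table's limits.** Each internal limit is the midpoint of adjacent target days.

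- HZN-825 block, Week 52/68: (365 + 477)/2 = 421.
- HZN-825 block, Week 68/80: (477 + 561)/2 = 519.
- OLE block, Week 68/80: (113 + 197)/2 = 155.
- The rule was not applied between OLE Baseline and Week 68, where it gives (1 + 113)/2 = 57.

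**2. Put both blocks on one scale.** Study day = (study day of first open-label dose) + (OLE day) − 1. With the first dose on Day 365:

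| OLE day | Study day | OLE-Baseline block | HZN-825-Baseline block |
|---|---|---|---|
| 2 | 366 | Week 68 | Week 52 |
| 57 | 421 | Week 68 | Week 52 |
| 58 | 422 | Week 68 | Week 68 |
| 155 | 519 | Week 68 | Week 68 |
| 239 | 603 | Week 80 | Week 80 |
| 323 | 687 | Week 92 | Week 92 |
| 324 | 688 | Week 104 | Week 104 |

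The only structural mismatch is OLE Day 2 to 57. If the Week 52 visit falls at the edge of its tolerance, the last affected day is 421 − 358 + 1 = OLE Day 64 or 421 − 372 + 1 = OLE Day 50.

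**3. OLE-Baseline analysis.** A value on OLE Day 2 to 57 lies 113 − 57 = 56 to 113 − 2 = 111 days before target. Any FVC on OLE Day 58 to 155 is nearer, since 113 − 58 = 55 and 155 − 113 = 42. The early value is therefore used as Week 68 only if the subject has no later FVC through OLE Day 155. By comparison, the first Core window also opens on Day 2, but its target is Day 29, so a value can be at most 27 days early.

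**4. HZN-825-Baseline analysis.** Let the Week 52 FVC and first open-label dose fall on Day w, and a later FVC on OLE Day d, which is Day w + d − 1.

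- If w is 365 to 372, the later value is always further from Day 365 and never wins.
- If w is 358 to 364, the later value wins or ties, and a tie goes to the later value, when (w + d − 1) − 365 ≤ 365 − w, that is d ≤ 731 − 2w.
- w = 358 gives d ≤ 15 and w = 364 gives d ≤ 3.

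Example: Week 52 FVC on Day 358 and another on OLE Day 15, which is Day 372. Both are 7 days from target, so the post-dose value is used.

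Over w = 358 to 372 and every OLE day up to Day 421 there are 840 day combinations. The later value is chosen in 14 + 12 + 10 + 8 + 6 + 4 + 2 = 56 of them (6.7%). This is a count of calendar cells, not a probability. Otherwise the later value becomes Week 52 only if the Week 52 FVC is missing or invalid.

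**The case against.** Much can be said for leaving the table alone. Both primary Extension endpoints are changes to Week 104, where the windows agree. The analyses are descriptive (SAP section 6.2.1). Extension entrants complete the Week 52 visit, and protocol section 9.3.2.1 requires the Week 52 assessments even of those who stopped Core drug early, so the true Week 52 value normally wins. Subjects who stop open-label drug are asked to stay for scheduled visits. Opening the first window on Day 2 keeps every observation in use, and removing these values could drop the only post-baseline FVC of some early leavers. A start at OLE Day 58 matches Day 422 only when the first dose is on Day 365; over the visit tolerance, Day 422 is OLE Day 51 to 65.

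All of this is correct, and it makes the point a minor one. It does not remove the contradiction or the cases in which the rules, followed literally, give a mislabelled value. The point about alignment bears on how the fix is written.

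A reader might infer three stronger claims that the documents do not support:

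- **That early open-label values generally pass as end of Core.** They do so only under the conditions in step 4. The Core analysis itself is protected by its stop at the first open-label dose.
- **That the primary Extension endpoints are mis-windowed.** They are not. An early value can reach the Week 104 model estimate only indirectly, as a Week 68 input to the OLE mixed model.
- **That the Week 68 decline is made to look smaller.** This assumes that early leavers decline at the average rate. They may be declining faster, and the documents give neither an open-label decline rate nor a share of early leavers.

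**Conclusion.** The inconsistency is real and limited. An FVC on OLE Day 2 to 57 (Day 366 to 421 with the first open-label dose on Day 365) is Week 68 in one block and Week 52 in the other.

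In the OLE-Baseline analysis, a subject without a later FVC through OLE Day 155 contributes it as the Week 68 change in the by-visit summary. It is also input to the OLE mixed model, on the reading that the model takes windowed values as section 3.8 describes. In the HZN-825-Baseline analysis it is used as Week 52 only when the true value is missing or invalid, or was taken before Day 365 and is no closer to target.

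The number of subjects affected, and the direction and size of any effect at Week 68, cannot be derived from the documents. It is worth correcting for consistency; no inferential result depends on it.

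**What to change.** Amend Table 1 and one sentence of SAP section 3.8:

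- End the HZN-825-Baseline Week 52 window at the Core Phase end date, as in the Core block, using only pre-dose values on the day of the first open-label dose.
- Start the OLE-Baseline Week 68 window at OLE Day 58, following the table's midpoint rule.
- Define the HZN-825-Baseline windows from Week 68 onward by OLE day (58 to 155, 156 to 239, 240 to 323, 324 and later). The two blocks then agree whatever the date of the Week 52 visit. This is workable because the analysis set for the extension and combined periods (section 3.1.4) contains only subjects with an open-label dose.
- List values on OLE Day 2 to 57 in both blocks without analysing them, and reword the statement that every observation is placed at a visit.

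The cost is a few table cells and one sentence. The downside is that a few early-withdrawal FVCs are listed rather than analysed, which may take some early leavers out of the OLE mixed model; the SAP should say so.
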